- Depressive Symptoms with PHQ-9 score ≥ 5
- Not suicidal (PHQ-9 question 9 score ≥ 2)
- Not severely depression (PHQ-9 score ≥ 20)
- Not Pregnant or Breastfeeding
- Provision of written informed consent
- Not receiving ART at study entry
- Outpatient, not requiring hospitalization

Non-depressed control group will have PHQ-9 < 5 and not suicidal but otherwise identical.

Screening: We will screen participants newly presenting to clinic (<3 months). We will check PHQ-9 score to evaluate for eligibility and record the baseline CD4 count. We will also record baseline demographics including biological sex and age. We will record all screened in screening log. We will also ask all women the date of their last menstrual period, their last pregnancy, and do a pregnancy test on all women ages 18-50 if otherwise eligible.

Baseline Measurements: Those with PHQ-9 ≥ 5 and ≤ 19 will be invited to consent as well as a non-depressed (PHQ-9 < 5) control group otherwise meeting enrollment criteria. Those consenting will have PHQ-9 recorded as well as Hamilton Rating Depression Scale,¹⁰ which has not been previously validated in Uganda. We will compare depression prevalence between the two scales. Of enrolled participants (PHQ-9 score > 5), We will collect plasma and cryopreserve at -80C for biomarker quantification. We will record the medications the participants are prescribed including antidepressants and ART. I will administer a questionnaire about relevant social factors to depression including a validated social support scale as well as the Stress and Adversity Inventory (STRAIN).

Week 12 Measurements of those depressed: At 12 weeks we will assess for depression using PHQ-9. We will record the medications the participants are on including antidepressants and ART. This is primarily a safety check. Those not depressed will not be contacted.

26 Week Follow Up Including HIV Viral Loads: We will again assess for depression using PHQ-9. We will record medications the participants are taking and measure plasma cytokines/biomarkers. We will again administer the social factor questionnaire including a validated social support scale as well as the STRAIN stress inventory tool. HIV plasma viral load will be checked per National Ugandan HIV guidelines. We will collect these data via review of the electronic medical record.

Cytokine measurement will be performed at baseline and 26 weeks.

Statistical Analysis: Our analysis will focus on:

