1.2. Background and Rationale

Depression in HIV is common and causes poor HIV outcomes. Depression prevalence in HIV-infected persons ranges from 13 to 78% as compared to 5% in the general population.^{16, 17} Adherence to antiretroviral medication and subsequently viral suppression is a life-saving treatment in HIV.¹⁸ However, depression has been shown to reduce engagement in care as well as adherence to medication.¹⁹ There is also evidence that depression is associated with poorer levels of viral suppression and even mortality.^{20, 21}

Depression in HIV has negative public health implications. Depression decreases the likelihood that people will engage in HIV care, adhere to treatment, and respond to HIV therapy. Those with depression and HIV are less likely to return to health and remain more likely to transmit the virus.^{22, 23} Because of this, treatment of HIV is an important key to prevention; lower rates of engagement in and adherence to HIV treatment due to depression means others remain at risk.^{24, 25}

Growing evidence shows depression has an inflammatory component. Depression has higher prevalence in neuroinflammatory disorders including stroke, diabetes, and HIV.¹⁴ These conditions alter the blood brain barrier allowing for infiltration of immune cells and increased cytokine signaling. While many diseases make people chronically ill such as hepatitis B, only some have increased prevalence of depression such as HIV. This observation does not suggest that the psychosocial impacts of chronic life-threatening illness do not contribute to depression but does imply that neuroinflammatory effects in diseases such as HIV can be additive or synergistic in the pathogenesis of depression.

Depression in HIV, even when participants have virologic suppression, is often resistant to standard psychiatric treatment, and treatment for depression among people living with HIV is understudied. While there are many treatment modalities for depression, a significant proportion of patients do not respond to treatment.²⁶ Also, while there are a few studies looking at treatment of depression specific in HIV, the data are scant.^{27, 28} More work on depression treatment in those with HIV is needed, particularly in low-income countries in sub-Saharan Africa given the high prevalence of HIV.

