5.2. Study Period

Those individuals with mild to moderately-severe depression who consent will be enrolled into the study. They will be asked to provide a plasma sample. We will also administer the Hamilton Depression Scale, a stress assessment using the STRAIN, and a social factors questionnaire. I will also as an extra voluntary measure invite the participants to give a CSF sample via lumbar puncture. This will be requested at baseline and at 26 weeks. Those willing will have an extra consent and receive extra compensation of 100,000 Ugandan shillings. This is in addition to the 10,000- 30,000 Ugandan shillings for transportation every visit.

Follow-up Visit

Week 12 Measurements: At 12 weeks we will again assess the depressed groups for depression using PHQ-9. This is primarily a safety check. We will record the medications the participants are on including antidepressants and ART.

26 Week Measurements: We will again assess for depression using PHQ-9. We will record medications the participants are taking and measure plasma cytokines/biomarkers. We will again administer the social factor questionnaire including a validated social support scale as well as the STRAIN tool. HIV plasma viral load will be checked per National Ugandan HIV guidelines. I will collect these data via review of the electronic medical record.

Those who gave a CSF sample at enrollment will again be invited to give another sample. This will again have an extra consent and receive extra compensation.

Cytokine measurements: We will perform cytokine assays at baseline and 26 weeks using linear regression.

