5.3. Subject Withdrawal

Subjects may withdraw from the study at any time at their own request, or they may be withdrawn at any time at the discretion of the investigator or sponsor for safety or behavioral reasons, or the inability of the subject to comply with the protocol required schedule of study visits or procedures.

If a subject does not return for a scheduled visit, every effort should be made to contact the subject. At enrollment they will provide 3 phone numbers. The participants will be called to remind them of their appointments and will be called if they do not return. In any circumstance, every effort should be made to document subject outcome, if possible. The investigator should inquire about the reason for withdrawal and follow-up with the subject regarding any unresolved adverse events (AEs).

If the subject withdraws from the study, and also withdraws consent for disclosure of future information, no further evaluations should be performed, and no additional data should be collected. The sponsor may retain and continue to use any data collected before such withdrawal of consent.

Table 1. Schedule of Study Events

Week	0	12	26
Patient Health Questionnaire-9 (PHQ-9)	X	X	X
Hamilton Depression Rating Scale	X		X
Plasma Inflammatory Biomarkers	X		X
AM Cortisol Levels	X		X
Stress using STRAIN	X		X
Social Factors Questionnaire	X		X
Group Support Psychotherapy		→	
HIV Viral Load (via chart review)			X

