8.2. Analysis of Endpoints

- 1) *Effect of Group Support Psychotherapy:* We will compare the proportion of baseline depression with the proportion of persistent depression at week 26. We will use the PHQ-9 as a continuous variable, with changes from baseline to week 26.
- 2) *Effect of biomarkers on persistent vs. resolved depression:* We will compare those with persistent depression (PHQ-9 ≥ 5 at week 26) versus resolved depression (PHQ-9 < 4 at week 26). We will assess baseline demographic and HIV parameters as well as log₂-transformed plasma cytokines from week 0, week 26, and the change in biomarker values from week 0 to week 26. We will use Benjamini-Hochberg adjustment for multiple comparisons for the biomarkers unrelated to our *a priori* hypothesis (i.e. IL-6 association with persisting depression). If the distribution between groups is unbalanced for an important factor (e.g. age, sex as biological variable, anti-depressant use, HIV viral load), we will adjust as needed for differentially distributed variables between the cohorts. We will consider sex as a biological variable in our analyses, considering differential effects in women vs. men.
- 3) *Effect of biomarkers on depressed vs non-depressed control group:* We will compare those never depressed (PHQ-9 < 5) and those depressed at baseline and at 26 weeks. We will also group those never depressed with those with resolved depression (PHQ-9 < 5 at week 26) and compare with those with persistent depression (PHQ-9 > 4 at week 26). We will assess baseline demographic and HIV parameters as well as log₂-transformed plasma cytokines from week 0, week 26, and the change in biomarker values from week 0 to week 26. We will use Benjamini-Hochberg adjustment for multiple comparisons for the biomarkers unrelated to our *a priori* hypothesis (i.e. IL-6 association with persisting depression). If the distribution between groups is unbalanced for an important factor (e.g. age, sex as biological variable, anti-depressant use, HIV viral load), we will adjust as needed for differentially distributed variables between the cohorts. We will consider sex as a biological variable in our analyses, considering differential effects in women vs. men.

*Depression Defined as PHQ-9 score 5-19 (severely depressed excluded)

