- 5) *Baseline Cytokine Analysis:* As a secondary outcome, subjects will be categorized into baseline groups of mild depression versus moderate or above depression. We will compare baseline plasma biomarker levels by group via linear regression of \log_2 transformed data. Any demographic covariates associated with depression will be included in the regression model. We will also compare by 9 am cortisol levels. We will assess whether age or sex are associated with biomarker responses.
- 6) *Virologic Outcomes:* As a secondary outcome, proportions of those with 26-week virologic suppression will be correlated by those with persisting depression vs. resolved using Fisher's Exact test.
- 7) *Depression Scale Comparison:* We will compare prevalence of depression using the PHQ-9 and the HDRS. We will compare the proportions of those depressed at baseline and 26 weeks using McNemar's test.
- 8) *Social Factors and Stress Assessment:* We will analyze social factors and the STRAIN stress and adversity tool scores by baseline depression groups as well as those with persistent depression at 26 weeks using linear regression.

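### Viral suppression is read from routine charts with no rule for absent results, so the item 6 comparison can be biased in a direction that is not assured

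*Combined protocol and SAP*

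**What the plan says.** Item 6 of section 8.2 (item 5 in the synopsis) makes virologic suppression a secondary outcome: "proportions of those with 26-week virologic suppression will be correlated by those with persisting depression vs. resolved", with Fisher's exact test as the method.

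The viral load is a routine-care test. Section 5.2 states that "HIV plasma viral load will be checked per National Ugandan HIV guidelines", then "I will collect these data via review of the electronic medical record". Table 1 (section 5.3) lists it at week 26 only, by chart review.

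Item 6 gives no denominator, no time window, no suppression threshold and no rule for a participant whose chart holds no result. No such rule for viral load appears elsewhere.

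The groups are defined by the week-26 PHQ-9 (section 8.2, item 2). Section 1.2 says that "depression has been shown to reduce engagement in care as well as adherence to medication".

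Objective 3 in section 2.1 asks a different virologic question, whether group psychotherapy improves suppression at 26 weeks. Section 8.2 plans no analysis of suppression by cohort.

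**The concern.** Fisher's test on a two-by-two table cannot place a person who has no result unless a rule assigns one. With no rule, the analysis becomes complete-case by default.

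That would matter little if results were absent at random. The protocol's own rationale points elsewhere. If depression weakens engagement with the clinic, and the clinic is the only source of the viral load, disengagement can both worsen suppression and remove the evidence of it. Absence of a result may then be tied to both variables being compared.

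At stake is a named secondary outcome. A null result could reflect who was tested rather than who was suppressed, and the denominator would be settled after the data are seen.

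**Working it through.** **1. Group sizes.** The documents give no sample size or power for suppression. The only stated figure is 168 for the IL-6 comparison (section 8.1: delta 0.5, 80% power, two-sided 0.05, 25% persistent). Reading delta as 0.5 SD and the split as 1:3, a two-sample calculation gives 42 persistent and 126 resolved, total 168, which matches. I use 42 and 126 below. The 25% is stated for the psychotherapy group; applying it to both cohorts is an assumption.

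**2. Assumed rates.** The documents give none for suppression or for missing viral loads. I assume true suppression s = 75% (persistent) and 90% (resolved): gap 15 points, odds ratio (0.75/0.25)/(0.90/0.10) = 0.33. Let m be the share with no result and u the share of those who are unsuppressed.

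**3. Complete-case suppression** = (s − m(1 − u))/(1 − m).

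Example with m = 20% v 5% and u = 70%:
- persistent: (0.75 − 0.20 × 0.30)/0.80 = 0.8625
- resolved: (0.90 − 0.05 × 0.30)/0.95 = 0.9316
- gap: 6.9 points

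| Missing, persistent v resolved | u | Complete-case | Gap (points) | Odds ratio |
|---|---|---|---|---|
| none | – | 75.0% v 90.0% | 15.0 | 0.33 |
| 20% v 5% | 50% | 81.3% v 92.1% | 10.9 | 0.37 |
| 20% v 5% | 70% | 86.3% v 93.2% | 6.9 | 0.46 |
| 10% v 5% | 70% | 80.0% v 93.2% | 13.2 | 0.29 |
| 5% v 5% | 70% | 77.4% v 93.2% | 15.8 | 0.25 |

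In the 20% v 5% rows the odds ratio moves toward 1. In the last two it moves away from 1, and in the last the gap widens as well.

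**4. Why the direction varies.** The observed odds ratio equals the true one multiplied by

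(retention of suppressed persistent × retention of unsuppressed resolved) / (retention of unsuppressed persistent × retention of suppressed resolved).

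If missingness depends on depression group alone, on suppression alone, or on both acting multiplicatively on retention, this factor is 1 and the odds ratio is unbiased. Loss tied to suppression can still shrink the gap in points and reduce power. The odds ratio moves toward 1 only when unsuppressed people are lost disproportionately in the persistent group.

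**5. Power.** Exact Fisher power is 61% with complete data at 42 v 126. With 20% v 5% missing (34 v 120 left) it is 41.5% at u = 50% and 24% at u = 70%. From 50 v 150 (25% of the 200 to be enrolled), complete-data power is 69%.

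**6. Counting no result as not suppressed** gives s − m(1 − u). With 20% v 5% missing:
- u = 50%: 65.0% v 87.5%, gap 22.5
- u = 70%: 69.0% v 88.5%, gap 19.5

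The complete-case gap (10.9 or 6.9) and this one lie on either side of the true 15.

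**7. The same rule with no true difference.** Let suppression be 90% in both groups, with 20% v 5% missing for reasons unrelated to it. Complete-case is 90% v 90%. Counting missing as failure gives 0.90 × 0.80 = 72.0% v 0.90 × 0.95 = 85.5%, and Fisher's test at 42 v 126 rejects about 45% of the time.

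**The case against.** **Direction.** A reader might infer that the association is biased toward none. The documents do not support that as fact. They state no direction and no missingness rates, and steps 3 and 4 show that it depends on the pattern assumed. The 20% v 5% split has no anchor. Section 8.1 plans for up to 5% loss to follow-up; the 21.7% dead or lost in section 1.2 comes from a different cohort, of cryptococcal survivors. This part of the objection stands.

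**Who is in the table.** Item 6 groups people by the week-26 PHQ-9, so everyone in it was assessed at week 26. Those who left the study earlier have no group, and no viral-load rule can restore them there. This also stands. What remains exposed in item 6 is the set assessed at week 26 but lacking a chart result. Only the cohort comparison under Objective 3, where cohort is known at entry, can include everyone enrolled.

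**Silence is not a rule.** The plan never says that only people with a result will be tested. That is an inference, but a sound one, since the test needs a result and nothing supplies one.

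**Mitigation.** Section 5.3 provides for three phone numbers, calls to non-returners and documenting outcomes. Section 6.1 has all charts checked, and the monitoring committee reviews completeness and losses (section 8.3). These may reduce missingness but do not say how the remainder is analysed.

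**The remedy can mislead.** Step 7 shows a false association created by counting missing as failure, and at u = 50% that analysis misses the true gap by 7.5 points against 4.1 for complete-case. This is a reason to show both and let neither replace the other.

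**Conclusion.** The gap in the plan is real. Suppression is ascertained only from routine charts, absent results have no rule, and the protocol's own rationale makes it plausible that absence depends on both depression and suppression. The default Fisher test can therefore be biased. Bias toward no association is plausible if unsuppressed, persistently depressed people are lost disproportionately, but it is not assured.

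The size is unknown. The gaps of 6.9 to 15.8 points around a true 15, and the fall in power from 61% to 24% in the worst case shown, are illustrations under assumed rates and not forecasts. Confidence in the magnitude is low; that the rule is missing is plain. The outcome is secondary and unpowered, but the correction is cheap and should be made.

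**What to change.** In section 8.2, item 6, and the matching synopsis item:

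- State the suppression threshold and the time window within which a chart result counts as week 26.
- Report, by depression group, the number with no chart viral load in that window.
- Keep the complete-case Fisher test, and add a pre-specified sensitivity analysis counting no result as not suppressed among those with a week-26 PHQ-9. Report separately how many have no week-26 PHQ-9 and so no group.
- Add the Objective 3 comparison of suppression between the observational and intervention cohorts, with the same pair of analyses over all enrolled depressed participants.
- Treat the two results as sensitivity analyses, and call the finding inconclusive if they disagree. Define disagreement in advance.

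The cost is a row of missing counts, one sensitivity analysis and one cohort comparison, with no new visits, samples or participants. The downside is that counting missing as not suppressed can overstate failure, for instance when a clinic test was only late. It can also create a false difference when missingness differs by group for reasons unrelated to suppression. It therefore sits beside the complete-case result and does not replace it.

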8.3. Safety Analysis

Data and Safety Monitoring Plan

1.0 Introduction: This document describes the Roles and Responsibilities of the Data Monitoring Committee (DMC) convened to monitor the clinical study.

2.0 Composition: This DMC shall have the composition described below. As DMC meetings will be at least annually, the DMC shall have a quorum minimum of three members and the statistician to be required for each DMC meeting. All members have previous experience with clinical trials and/or clinical studies experience with cryptococcal meningitis (Table 1). As the intervention is an open label study, members of the team will participate in the DMC along with external members.

Table 1. DMC Membership

Name	Role	Relevant Experience
[name]	Statistician	Multiple HIV-related trials, U of MN
[name], PhD	Member	Psychiatrist, U of MN
[name], MMed	Member	Multiple clinical trials, Mbarara Univ.
[name]	Member	Multiple AIDS-related clinical trials, Mbarara Univ.
[name]	Member	Epidemiologist, U of MN

Additional observers will participate as possible. Observers are non-voting members of the DMC. Observers will receive communications on DMC reports and recommendations.

3.0 Roles and Responsibilities: It is the role of the DMC to protect trial subjects and to provide impartial advice and assistance to the Principal Investigator regarding the conduct and continuation of the study, so as to protect the validity and credibility of the trial. The DMC will have access to the clinical protocol, interim data, adverse event reports, clinical monitoring reports, annual and/or progress reports submitted to the IRB and/or Regulatory Agency, and correspondence between the Principal Investigator and either the IRB or any Regulatory Agency of competent jurisdiction.

The specific roles of this DMC will be as follows:

- Assess data quality, including completeness.
- Monitor compliance with the protocol by participants and investigators.
- Monitor recruitment progress and losses to follow-up.
- Monitor evidence for treatment differences in the main efficacy outcome measures.
- Monitor evidence for treatment harm (SAE's).
- Advise on protocol modifications suggested by investigators or sponsors.
- Recommend trial continuation or termination as appropriate.

4.0 Relationships

4.1 DMC, Principal Investigator, and other Trial Oversight: The DMC shall provide an independent advisory role with investigator input. The DMC will make recommendations to the PI and/or oversight committees regarding trial conduct or continuation. As the trial is open-label, the PI and co-investigators will participate as observers to the DMC, providing their clinical insights. DMC reports will be provided to the oversight IRBs.

4.2 Conflicts of Interest: DMC members shall disclose potential competing interests, both financial and intellectual. None have a conflict of interest at present.

5.0 DMC Meeting Structure and Frequency

5.1 Meeting Structure: DMC Meetings will be held in an open format, as this is an unblinded interventional trial. First, demographic data and trial progress will be discussed. Quality Assurance and Compliance issues may be discussed in this session, and this session is open to investigators, sponsors, funder, patient advocates, and others as appropriate. Open sessions will be followed by closed sections in which only the DMC members, DMC observers, statistician, secretary and specifically invited guests will attend. In closed sessions the outcomes data will be assessed and recommendations formulated. DMC meetings will be conducted by teleconference / Skype.

5.2 Meeting Frequency: The DMC will meet based on the pace of subject recruitment. Initial reviews will be after ~33% and ~66% participants have enrolled into the protocol and have ≥ 12 weeks of data for review.

5.3 Meeting Notes: Meeting notes will be prepared after each DMC meeting.

5.4 Attendance: Members are expected to attend all meetings either in person or by teleconference. A quorum for recommendations/decision making shall be three members and the statistician. Members who fail to attend two consecutive meetings may be removed from the DMC and replaced.

6.0 Data Analysis: The PI will prepare an initial report. The DMC statistician will also perform an independent analysis appropriate to the data presented as per the statistical plan in the protocol. For interim analysis, the primary considerations are:

- Enrollment
- Data completeness.

- Compliance with the protocol by participants and investigators.
- Monitor evidence for treatment differences in the main efficacy outcome measures.
- Monitor evidence for unintended harm(s) or unintended HIV disclosure

